The safety and efficacy of systemic thrombolysis therapy using Actilyse® in patients with ischemic stroke have been proven in a number of large randomized placebo-controlled clinical trials (NINDS, ECASS I, II, III, ATLANTIS), as well as the SITS-MOST and SITS-ISTR registers.

In addition, a high frequency of hemorrhagic transformation (6-23.8%) and a high 3-month mortality rate (18.2%) were noted in some studies with alteplase, which, according to the researchers, is associated with an initially high neurological deficit.

In this regard, the search for new thrombolytic drugs that can improve the efficacy and safety of thrombolytic therapy is an important scientific and economic task.

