– a bolus and bolus+infusion i.v. injection of Fortelyzin® at a dose of 10 mg in comparison with Actilyse® in patients with acute myocardial infarction with ST-segment elevation (STEMI) showed the efficacy of the study drug comparable to that of Actilyse®;

– it is recommended to increase the dose of Fortelyzin® to 15 mg, administered according to the two schemes: the first scheme: 10 mg bolus + 5 mg bolus with an interval of 30 minutes; the second one: 10 mg bolus + 5 mg infusion for 30 minutes.

The further study assessed a bolus and bolus-infusion of Fortelyzin® at a dose of 15 mg vs. Actilyse® according to the Protocol "An open-label, prospective study of tolerability and efficacy of Fortelyzin® vs. Actilyse® in patients with acute myocardial infarction (phase III)", the authorization of Roszdravnadzor No. 196 dated 28.04.2010.

A total of 90 people were screened in 6 clinics, and 41 patients in the Fortelyzin® study group and 13 patients in the Actilyse® study group were included in the study.

In the Fortelyzin® group, a combination of bolus + infusion was administered to 21 patients, and 20 patients received a double bolus dose.

Assessment of the tolerability of the study drug revealed no serious adverse events (SAE) or hemorrhagic stroke in any of the groups observed. There was one adverse event in the form of "no-reflow" syndrome in the Fortelyzin® group and one bleeding in the Fortelyzin® group (considered as not related to the drug administration) and in the Actilyse® group (related to the drug administration).

There were no allergic reactions, nausea, and vomiting after administration of the drugs in both groups of patients. The maximum drop in blood fibrinogen on the first day after administration of Actilyse® was 38 %, and after administration of Fortelyzin® - only 7 %. The difference is statistically significant.

There was no decrease in blood pressure, increased pulse, and heart rate in both groups of patients.

Thus, the clinical study of bolus and bolus+infusion administration of Fortelyzin® showed their comparable tolerability with Actilyse® in STEMI patients.

Direct and indirect methods were used to assess the blood flow through the coronary arteries.

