12. SAFETY ASSESSMENT

- Safety endpoint - overall mortality on day 90.
- Safety endpoint - hemorrhagic transformation (all cases).
- Safety endpoint - symptomatic hemorrhagic transformation (as defined by ECASS III).
- The number of SAE and AE by organs and systems.

The assessment of safety is based on the number and severity of adverse events that may occur in the course of the trial. The drug is considered as well tolerated if no severe adverse events are registered during the trial (fatal outcome or life-threatening conditions of the patient), which, according to the Investigator, may be associated with the application of the drug studied.

Adverse events

Adverse event (AE) is any unfavorable medical occurrence in a patient or clinical trial subject administered a pharmaceutical product, which may not have a causal relationship with its use. Thus, an adverse event can be any adverse symptom (including deviation of the laboratory value from the norm), a complaint, or a disease, the time of occurrence of which does not exclude a causal relationship with the use of the medicinal product, regardless of the presence or absence of such communication.

Information about adverse events should be collected at each visit by interviewing the patient, as well as during physical examination and evaluation of laboratory and instrumental data. All adverse events that occur during the trial should be evaluated and documented.

When registering an adverse event, the following information should be reflected, if possible:

- the exact time of AE occurrence и разрешения
- the nature of the adverse event
- severity (mild, moderate, severe)
- causal relationship with the study drug
- whether the adverse event is serious
- actions taken (whether AE required any therapeutic measures)
- outcome

Adverse Event Grading:

- **Mild:** the presence of signs or symptoms that do not affect daily activities.
- **Moderate:** event has sufficient intensity to interfere with daily activities.
- **Severe:** inability to work or perform daily activities.

The connection between the development of an adverse event and the use of the study drug is determined by the WHO scale:

- **Certain:** Clinical manifestations of unforeseen adverse reaction (UAR), laboratory findings deviations that occur during the period of drug administration, can not be explained by the presence of existing diseases and the influence of other factors.

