18. STATISTICAL ANALYSIS OF RESEARCH MATERIALS

For Statistical Analysis R 3.5.1 package will be used.

Normally distributed variables will be described as mean (SD), ordinal variables as median (IQR), and categorical variables as number and percentage per category. For calculation of significant differences between proportions, we shall use the χ^2 method and for medians the Mann-Whitney U test (with a two-sided 5% level of significance). Ninety-five percent confidence intervals will be calculated for quantitative data.

The primary outcome and other continuous variables will be analyzed with a linear regression model. Binary variables will be tested using logistic regression models adjusted for the same stratification variables, p-values for the difference between treatment groups will be extracted from these models.

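### Section 18 plans no interval or upper bound on the between-arm difference for the three binary safety endpoints, so a non-significant test cannot show comparable safety

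*Combined protocol and SAP*

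**What the plan says.** The trial design entry of the Protocol Summary describes a parallel-group non-inferiority trial covering efficacy and safety, and Section 8 repeats the non-inferiority framing. Section 6 makes safety relative to Actilyse one of two objectives. Section 12 names three binary safety endpoints. The first is "Safety endpoint - overall mortality on day 90"; the others are hemorrhagic transformation of any kind and symptomatic transformation by the ECASS III definition.

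Section 18 is the whole analysis plan:

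- Categorical variables are described by number and percentage.
- Proportions are compared by chi-square at a two-sided 5% level.
- Binary variables also go into logistic regression, from which "p-values for the difference between treatment groups will be extracted from these models".
- The only sentence on intervals is "Ninety-five percent confidence intervals will be calculated for quantitative data".

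No section gives a risk difference, interval, margin or decision rule for a comparative safety endpoint. The sample size in Section 17 rests on the 16-point efficacy margin alone. Section 12 does contain a tolerability rule, but it concerns severe events that the investigator attributes to the drug and does not compare the arms.

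**The concern.** A test of no difference answers whether harm has been detected. A non-inferiority question about safety asks how much excess harm can be ruled out, and only an interval or an upper bound answers that. If the test is not significant, the planned comparative output is a p-value above 0.05 beside two percentages. The reader is not told what excess in deaths or intracranial bleeding remains compatible with the data. For a thrombolytic these are the harms that matter most, and the trial was not sized for them.

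**Working it through.** **The plan's own figure.** Section 17 uses 54.8% in both arms, a margin of 16 points, a two-sided 5% level (z = 1.96) and 80% power (z = 0.8416):

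n = (1.96 + 0.8416)² / 0.16² × 2 × 0.548 × 0.452 = 151.9, so 152 per arm.

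Then 152 × 1.1 = 167.2, so 168. Both stated figures reproduce. They concern efficacy only.

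**Inputs for safety.** Section 1 gives the only alteplase rates in stroke: "a high frequency of hemorrhagic transformation (6-23.8%) and a high 3-month mortality rate (18.2%) were noted in some studies with alteplase". It gives no rate for symptomatic transformation, so 3% is assumed, with 2% and 5% as a range. The arms have 152 patients (after the planned dropout) or 168 (all randomized).

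**Method.** All outcome pairs of two independent binomials were enumerated. Rejection means an uncorrected chi-square significant at two-sided 5% in the harmful direction, and the miss rate is 1 minus that probability.

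A normal-approximation check for mortality, 18.2% to 27.3% at 168 per arm:

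- Pooled rate 0.2275. Null SE = √(2 × 0.2275 × 0.7725 / 168) = 0.0457.
- Alternative SE = √[(0.182 × 0.818 + 0.273 × 0.727) / 168] = 0.0455.
- Power = Φ[(0.091 − 1.96 × 0.0457) / 0.0455] ≈ 0.51, so the miss rate is about 0.49. Enumeration gives 0.484.

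| Endpoint, Actilyse to Fortelyzin | Missed, 168 per arm | Missed, 152 per arm |
|---|---|---|
| Mortality 18.2% to 27.3% (×1.5) | 48% | 52% |
| Mortality 18.2% to 36.4% (×2) | 3% | 5% |
| Any transformation 6% to 12% (×2) | 50% | 55% |
| Any transformation 6% to 18% (×3) | 6% | 9% |
| Any transformation 23.8% to 35.7% (×1.5) | 33% | 37% |
| Symptomatic, assumed 3% to 6% (×2) | 74% | 76% |

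For the symptomatic endpoint at 168 per arm, a doubling is missed in 83% at an assumed 2% and in 59% at an assumed 5%. A Yates correction would raise the miss rates: for example, mortality ×1.5 at 168 per arm goes from 48% to 54%.

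**What an interval would add.** Two illustrations at 168 per arm, with Newcombe 95% intervals:

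- 46 versus 31 deaths (27.4% versus 18.5%): p = 0.052, difference +8.9 points, interval −0.1 to +17.8.
- 12 versus 5 symptomatic bleeds (7.1% versus 3.0%): p = 0.08, difference +4.2 points, interval −0.7 to +9.4.

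Both are non-significant. Only the interval shows that excesses of nearly 18 and 9 points are not excluded.

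**Precision when the arms look alike.** The half-width at equal observed rates is about 1.96 × √(2p(1 − p)/n). At 168 per arm this is 8.2 points for p = 18.2%, 5.1 for 6%, 9.1 for 23.8% and 3.7 for an assumed 3%. The Newcombe upper limit is +8.3 points for 31 versus 31 deaths and +4.2 for 5 versus 5 symptomatic bleeds.

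**The case against.** The strongest reply has four parts.

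1. Counts and percentages will be reported by arm, so an excess would be visible and any reader could compute an interval. This is true. What is missing is a prespecified interval and a conclusion tied to it, not the raw information.
2. Safety is not judged by p-values alone. Section 12 has its tolerability rule, causality grading and TIMI/GUSTO grading of bleeds, and Section 7.5 allows early stopping for harm. This also stands, but none of it bounds the difference between arms.
3. The term quantitative data may be loose translation. The same section groups the binary primary outcome with continuous variables, so its labels are unreliable. Because it describes categorical variables separately, excluding proportions is the more natural reading, though not a certain one. If intervals for proportions were intended, the proposed text only makes that explicit.
4. Safety endpoints are seldom powered, and the Section 1 rates come from selected studies described as high, not from planning assumptions. This is fair, and no larger sample is asked for. Low power is the reason to report intervals.

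A reader might infer that the sponsor will declare comparable safety whenever the test is not significant. The documents contain no such rule. The nearest support is Section 2, where an earlier infarction study with 41 and 13 patients is said to have "showed their comparable tolerability with Actilyse® in STEMI patients". That is a different study in a different indication and sets no rule for this one. A reader might also infer that the tests miss most large harms. The table does not support this: the miss rate ranges from about 3% to over 80%, depending on the endpoint, the base rate and the size of the harm.

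**Conclusion.** The point holds as a gap in the stated analysis. The trial claims a non-inferiority design for safety, yet its only specified between-arm safety method cannot bound excess harm. The power for moderate harms is limited: about even odds of missing a 1.5-fold mortality rise from 18.2% or a doubling of transformation from 6%, and roughly one in three for a 1.5-fold rise from 23.8%. A doubling of mortality would almost always be detected. The symptomatic figures depend on an assumed rate. The conclusion that no interval is planned rests on reading quantitative data as excluding proportions. The gap can be closed by a reporting rule, so this is a cheap improvement and not a flaw in the design or sample size.

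**What to change.** Add to Section 18 text along these lines: *For day-90 mortality, any hemorrhagic transformation and symptomatic hemorrhagic transformation, the risk difference (Fortelyzin minus Actilyse) will be reported with a two-sided 95% Newcombe or Miettinen-Nurminen interval. The comparative safety statement will be based on the upper limit of that interval. A non-significant p-value will not be taken as evidence of comparable safety.* Keep the chi-square and logistic analyses as supplementary.

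The cost is a few sentences and three intervals in the report, with no new patients or data. The small downside is a more cautious safety statement: even with equal observed rates, the upper limit would be about +8 points for mortality and about +4 points at an assumed 3% symptomatic rate.

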	
 • Severe liver disease, including liver failure, cirrhosis, portal hypertension (with varicose veins of the esophagus), active hepatitis. • Acute pancreatitis. • Bacterial endocarditis, pericarditis. • Aneurysms of arteries, malformations of arteries and veins. Suspicion of exfoliating aortic aneurysm. • Neoplasms with an increased risk of bleeding. • Large operations or severe injuries within the last 14 days, minor surgery or invasive manipulations in the last 10 days. • Puncture of uncompensated arteries and veins during the last 7 days. • Prolonged or traumatic cardiopulmonary resuscitation (more than 2 min). • Pregnancy, obstetrics, 10 days after birth. • The number of platelets is less than 100,000/μL. • Blood glucose less than 2.8 mmol/l or more than 22.5 mmol/l. • Hemorrhagic diathesis, including renal and hepatic insufficiency. • Data on bleeding or acute trauma at the time of examination. • Seizures in the onset of the disease, if there is an uncertainty that the seizure is a clinical manifestation of ischemic stroke with a postictal residual deficiency.
Trial procedures:	
 • collection of anamnesis, physical examination, measurement of vital signs (respiratory rate, heart rate, blood pressure)

	
 assessment of neurological status according to generally accepted methods with the trial of cerebral, meningeal, and focal symptoms assessment of neurological status using NIHSS, which allows to quantify the severity of neurological deficits Brain CT or MRI performed within 40 minutes of the patient's admission to the hospital angiography of cerebral vessels (if necessary) duplex scanning of the major arteries of the head (if necessary) venous blood sampling for complete blood count (with platelet count) and biochemical blood analysis (with glucose level determination), coagulogram (INR, APTT, fibrinogen). The results of the tests should be obtained within 20 minutes from the moment the patient admitted to the hospital common urine analysis
Efficacy criteria:	
 The primary efficacy endpoint is a good functional recovery on day 90 (modified Rankin scale, mRS, 0-1 score). Secondary combined efficacy endpoint on day 90 – mRS (0-1) + NIHSS (0-1 score) + Barthel Index (BI) - 95 points or higher. Additional efficacy criterion – NIHSS score after 24 hours and after 90 days.

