11. EFFICACY ASSESSMENT

This trial involves a comparison group. Evidence of Fortelyzin® efficacy will be compared with the results of the application of Actilyse®.

Criteria for the efficacy evaluation of thrombolytic therapy

- The primary efficacy endpoint is a good functional recovery on day 90 (modified Rankin scale (mRS), 0-1 score).
- Secondary combined efficacy endpoint on day 90 – mRS (0-1) + NIHSS (0-1 score) + Barthel Index (BI) - 95 points or higher.
- Additional efficacy criterion – NIHSS score after 24 hours and after 90 days.

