17. CALCULATION OF SAMPLE SIZE

No multicenter randomized clinical trials of thrombolytic therapy in ischemic stroke have been conducted in the Russian Federation before. Available scientific literature is related to the pilot application of Actilyse® in a limited number of AIS patients (10-16 people) (V. I. Skvortsova et al., 2006, N. A. Shamalov, 2015). Thus, the data of the SITS-MOST international register and the results of randomized multicenter clinical trials of Actilyse® in comparison with placebo in patients with ischemic stroke were used as the basis for the sample size justification.

The calculation of the number required was carried out taking into account the capacity of 80 % and planning of a non-inferiority study in parallel groups [V. I. Sergienko, I.B. Bondareva "Mathematical statistics in clinical trials"; GEOTAR-Media, Moscow, 2006]. The null hypothesis (H_0) was that the thrombolytic therapy with Fortelyzin® is worse than the standard thrombolytic therapy with Actilyse®. This means that frequency of the primary efficacy criterion in the comparison group (P_{Actilyse}) is higher than in the group of the study drug ($P_{\text{Fortelyzin}}$), taking into account the "no worse" boundary (δ):

$$H_0: P_{\text{Fortelyzin}} - P_{\text{Actilyse}} \leq -\delta$$

The alternative hypothesis (HA) is that Fortelyzin® therapy is no less effective than the standard thrombolytic therapy with Actilyse:

$$H_A: P_{\text{Fortelyzin}} - P_{\text{Actilyse}} > -\delta$$

The calculation of the sample size for the "no worse" hypothesis, the primary criterion representing the proportion of respondents, and even 1:1 distribution in therapy groups is carried out according to the following formula [Chow S-Ch., Shao J., Wang H., "Sample Size Calculations in Clinical Research", 2003]:

$$n = \frac{(z_{1-\alpha} + z_{1-\beta})^2}{(\delta - \Delta)^2} [p_1(1 - p_1) + p_2(1 - p_2)]$$

where n – the number of patients in each of the groups compared;

p_1 – the proportion of **respondents** (reaching the primary efficacy criterion) in the group of the study drug;

p_2 – the proportion of **respondents** in the comparison group with Actilyse®;

$\Delta = p_1 - p_2$ – the expected difference between the proportions of respondents in the groups of the study drug and the comparison drug;

δ – “no worse” boundary

α and β – probabilities of type I and II errors, respectively;

$Z_{1-\alpha}$ and $Z_{1-\beta}$ – critical values of the standard normal distribution.

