The limit of clinical significance was chosen to be 16.9% and was calculated as follows.

The frequency of reaching the primary efficacy criterion in the thrombolytic therapy of ischemic stroke using Actilyse®, namely, the percentage of good functional recovery 3 months after thrombolysis (MRS – 0-1 score) according to the International Register (SITS-MOST) is 54.8 % (total number of patients is 6 483) (Wahlgren N et al., SITS-MOST investigators. Multivariable analysis of outcome predictors and adjustment of main outcome results to baseline data profile in randomized controlled trials; Safe Implementation of Thrombolysis in Stroke Monitoring Study (SITS-MOST). *Stroke* 2008; 39: 3316-3322).

The frequency of reaching the primary efficacy criterion when using placebo – the percentage of good functional recovery (MRS-0-1 score) in patients with ischemic stroke 3 months after thrombolysis, is on average 37.9%. This value was obtained according to the ECASS II, Atlantis, and ECASS III studies, where the favorable effect when using placebo was 36.6%, 32 %, and 45.2%, respectively (Hacke W et al, for the Second European-Australasian Acute Stroke Study Investigators. Randomized double-blind placebo-controlled trial of thrombolytic therapy with intravenous alteplase in acute ischaemic stroke (ECASS II. *Lancet* 1998;352:1245-1251),

(Clark W.M., et al., for the Atlantis Study Investigators. for the Second European-Australasian Acute Stroke Study Investigators. Recombinant tissue-type plasminogen activator for ischemic stroke 3 to 5 hours after symptom onset. The Atlantis Study: A Randomized Controlled Trial. *JAMA* 1999;282:2019—26),

(Hacke W, et al. "Thrombolysis with Alteplase 3 to 4.5 Hours after Acute

Ischemic Stroke". ECASS III The New England Journal of Medicine. 2008. 359(13):1317-1329).

Thus, the difference between a good clinical recovery in patients with AIS with the use of Actilyse® and placebo is $54,8\% - 37,9\% = 16,9\%$. Thus, the "no worse" boundary was set as 16%.

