Assuming equal proportions of reaching the primary efficacy criterion in the study drug group and the comparison drug group of 54.8% ($\Delta = 0$), with the established "no worse" boundary of 16% and demonstration at the bilateral significance level of 5%, the minimum number of patients included in the trial is estimated as 152 people in each therapeutic group to maintain 80% of the comparison power. Taking into account the possible 10% dropout, it is recommended to increase the sample size to 336 patients (168 patients in each group).

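### Section 18 treats the binary primary endpoint as continuous and never compares it with the -16-point non-inferiority boundary

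*Combined protocol and SAP*

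**What the plan says.** The endpoint is a yes/no outcome wherever it is defined. The Protocol Summary, under efficacy criteria, reads "The primary efficacy endpoint is a good functional recovery on day 90 (modified Rankin scale, mRS, 0-1 score", and Section 11 repeats it.

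Section 17 describes "planning of a non-inferiority study in parallel groups" and treats the endpoint as a proportion of responders. Its null hypothesis is that P(Fortelyzin) - P(Actilyse) is at or below -delta. It says that the "boundary was set as 16" per cent, and it bases the sample size on a "boundary of 16% and demonstration at the bilateral significance level of 5" per cent.

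Section 18 is the analysis section. It says:

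- "The primary outcome and other continuous variables will be analyzed with a linear regression model".
- "For calculation of significant differences between proportions, we shall use the" chi-square method, at a two-sided 5% level.
- Binary variables go to logistic regression, "adjusted for the same stratification variables, p-values for the difference between treatment groups will be extracted from these models".
- 95% confidence intervals are promised for quantitative data.

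Section 18 mentions no boundary, no non-inferiority test and no decision rule, and no other section supplies one.

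**The concern.** Sections 17 and 18 do not describe the same analysis. Section 17 asks whether a deficit of 16 points can be excluded. The methods that Section 18 gives for proportions and binary variables ask whether the two rates differ at all.

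The sentence on the primary outcome does not bridge the gap. If linear regression is applied to the raw mRS score, the estimate is on a scale where a 16-point margin in proportions has no meaning. If it is applied to a 0/1 responder indicator, it estimates a difference in proportions and could serve, but the plan states neither that coding nor the comparison with -16. The logistic models are also incomplete: they adjust for stratification variables that are called the same ones as before, yet none is named, and the randomisation in Section 8 mentions no strata.

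The primary conclusion is at stake. Of the stated tests of no difference, only a significant result favouring Fortelyzin would imply non-inferiority, and that is rare when the drugs are equally effective. The usual result with equal drugs is non-significance, which leaves the Section 17 hypothesis undecided. The step from Section 18 output to the Section 17 claim would then have to be settled once data exist, in an open-label trial.

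**Working it through.** **Inputs (Section 17).** Responder rate 54.8% in both arms, delta = 0.16, expected difference 0, two-sided 5%, 80% power, 1:1 allocation, 152 per arm before and 168 per arm after the dropout allowance.

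**1. Reproduce the sample size.** The formula is n = (z_alpha + z_beta)^2 x [p1(1-p1) + p2(1-p2)] / (delta - Delta)^2.

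- Two-sided 5%, delta = 0.16: (1.960 + 0.842)^2 x 2 x 0.548 x 0.452 / 0.16^2 = 151.9, so 152, as stated.
- Same level, delta = 0.169: 136.1, so 137.
- z = 1.645, delta = 0.16: 119.6, so 120.
- Dropout: 152 x 1.10 = 167.2, so 168, as stated.

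Of these variants, only a 16-point boundary with a two-sided 5% level gives 152. The trial was sized for a two-sided 95% interval compared with -16 points.

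**2. What the two kinds of analysis deliver.** Exact binomial enumeration over all pairs of counts, Actilyse rate 0.548, pooled chi-square without continuity correction:

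| Result | 152/arm | 168/arm |
|---|---|---|
| *True difference 0* | | |
| Chi-square significant, favouring Fortelyzin | 2.5% | 2.7% |
| Chi-square non-significant | 95.1% | 94.5% |
| Lower 95% limit above -16, Newcombe | 80.7% | 85.1% |
| Same, Miettinen-Nurminen | 80.6% | 85.1% |
| Same, Wald | 80.6% | 84.0% |
| Same, linear model on 0/1 outcome | 80.6% | 82.9% |
| Non-significant and clears -16 (Newcombe) | 78.2% | 82.4% |
| Non-significant and does not clear (Newcombe) | 16.9% | 12.1% |
| *True difference -16 points* | | |
| Chi-square non-significant | 20.5% | 14.9% |
| Lower 95% limit above -16, Newcombe | 2.55% | 2.75% |

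With the linear model on a 0/1 outcome, the two split rows are 78.2% and 16.9% at 152 per arm, and 80.2% and 14.3% at 168 per arm.

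**3. Two data sets that chi-square does not separate.** Take 168 per arm with 92 Actilyse responders (54.8%). The Newcombe lower limit is d - sqrt[(p1 - l1)^2 + (u2 - p2)^2], where l1 and u2 are the Wilson lower limit for Fortelyzin and the Wilson upper limit for Actilyse. Here u2 = 0.6210, so u2 - p2 = 0.0734.

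- 80 vs 92 responders: d = 0.4762 - 0.5476 = -0.0714 and l1 = 0.4021, so the limit is -0.0714 - sqrt(0.0741^2 + 0.0734^2) = -0.176. Chi-square p = 0.19. Non-inferiority is not shown.
- 86 vs 92 responders: d = 0.5119 - 0.5476 = -0.0357 and l1 = 0.4369, so the limit is -0.0357 - sqrt(0.0750^2 + 0.0734^2) = -0.141. Chi-square p = 0.51. Non-inferiority is shown.

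Both are non-significant, and the Section 17 conclusions are opposite.

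**The case against.** The best defence is that Section 17 already fixes nearly everything: the effect measure, both hypotheses, the boundary and the two-sided 5% level. Linear regression on a 0/1 indicator, with the 95% intervals that Section 18 promises for quantitative data, would give the required difference and limit. The next sentence of Section 18 sends binary variables to logistic regression, so the wording may be a drafting slip. The Protocol Summary and Section 20 also assign the analysis to an independent statistical expert.

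Some of this stands. An analyst who starts from Section 17 has limited freedom, and the linear model is a workable route. Several of the figures also do not measure harm done by Section 18:

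- About 95% non-significance under equality is what any valid two-sided 5% test gives.
- The 17% (or 12-14%) that are non-significant and miss the boundary are mostly the ordinary type II error of the correct analysis, and would remain after the fix.
- The 20.5% and 14.9% apply only if p > 0.05 were read as no worse, which the plan does not say.
- The 168-per-arm figures assume no dropout.

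The defence still does not close the gap. Section 17 states its hypotheses to size the trial and names no estimator, interval or decision rule. The interval sentence in Section 18 mentions neither proportions nor the boundary. By name the primary outcome falls under linear regression, by type under logistic regression, and neither sentence leads to -16 points. The plan does not say that the independent expert is blinded, and independence does not supply a missing rule.

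**Conclusion.** The concern holds, and the text should be corrected before the primary analysis. Section 18 misclassifies the binary primary endpoint, and its stated tests for proportions do not address the Section 17 null hypothesis. This is an error in the analysis text; the sample size is sound.

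The clearest measure of the gap is what each analysis can establish when the drugs are equal. A significant result favouring Fortelyzin arises in 2.5% of trials at 152 per arm (2.7% at 168). The boundary comparison succeeds in about 81% (83-85% at 168, depending on the interval method). These figures assume a true rate of 54.8% in both arms and complete outcomes at the stated size. The contradiction between the sections does not depend on those assumptions.

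**What to change.** Replace the sentence on the primary outcome with text such as:

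> Primary analysis: the difference in the proportion with mRS 0-1 at day 90 (Fortelyzin minus Actilyse), with a two-sided 95% confidence interval by [one method named in advance, e.g. Newcombe or Miettinen-Nurminen]. Non-inferiority is concluded only if the lower limit is above -16 percentage points. P-values for a difference are not used for this conclusion.

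A linear model on a 0/1 indicator would also answer the question if the coding and the comparison with -16 were written down. The choice of interval is secondary to having one rule.

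In the same edit:

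- Keep linear regression for variables that are truly continuous.
- Define or delete the reference to stratification variables, and label any covariate-adjusted difference in proportions (for example, for baseline NIHSS and age) as supportive.
- Reconcile the 16.9% that Section 17 first gives as its limit with the 16% that it then adopts. Use -16, since 152 per arm reproduces only with that value.

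The cost is Section 18 wording and a few lines of code, with no extra patients, visits or staff. By the Section 17 formula, power under this rule is 80.0% at 152 per arm and 83.8% at 168. Analysis population and missing mRS values are outside this point.
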